### 6.8 Management of Subjects Exhibiting Serotonin Syndrome

There is a theoretical chance that epacadostat could cause an increase in serotonin levels in the brain that might trigger SS (<http://www.nejm.org/doi/full/10.1056/NEJMra041867>) when administered in combination with other serotonergic agents. This syndrome has been most closely associated with use of MAOIs, Demerol®, linezolid, or methylene blue; all of these agents are prohibited during the study. Selective serotonin reuptake inhibitors (SSRIs) and serotonin/norepinephrine reuptake inhibitors (SNRIs) are permitted in the study. The following procedures will be implemented if subjects exhibit the signs/symptoms of SS described in Table 6, including tremor; hyperreflexia; and spontaneous, ocular, or inducible clonus, together with agitation, fever, diaphoresis, or muscle rigidity:

- Immediately interrupt epacadostat administration. Administration of other study drugs may continue.
- Immediately interrupt any SSRI or SNRI administration.
- Provide appropriate medical management of the subject until all signs/symptoms are resolved (eg, IV fluids and/or sympathomimetic amines for hypotension, benzodiazepines for agitation, administration of 5-hydroxytryptamine antagonists, such as cyproheptadine).

- If subject chooses to remain in the study, restart treatment with epacadostat after the SSRI or SNRI has been discontinued, no sooner than 5 half-lives have elapsed for the specific SSRI or SNRI in question and after resolution of signs/symptoms of SS. The SSRI or SNRI treatment MAY NOT be restarted.
- If subject chooses to withdraw from the study or must restart treatment with SSRI or SNRI, the subject should be scheduled for a follow-up visit. Treatment with SSRI or SNRI may be initiated 2 weeks after resolution of signs and symptoms of SS.

**Table 6: Sign and Symptoms of Serotonin Syndrome**

Tremor and hyperreflexia
Spontaneous clonus
Muscle rigidity, temperature > 38°C (100.4°F), and either ocular clonus or inducible clonus
Ocular clonus and either agitation or diaphoresis
Inducible clonus and either agitation or diaphoresis

**7. CONCOMITANT AND EXCLUDED THERAPIES**

**7.1 Concomitant Therapy**

The patient must be told to notify the investigational site about any new medications he/she takes after the start of the study drug. All medications (other than study drug) and significant non-drug therapies (including blood transfusions) administered during the study should be recorded.

Concomitant therapy includes any prescription medications or over-the-counter preparations used by a patient between the 7 days preceding the screening evaluation and the treatment discontinuation visit.

Patients who experience infusion-associated symptoms may be treated symptomatically with antipyretics (ibuprofen preferred), diphenhydramine, and/or cimetidine or another H2 receptor antagonist, as per standard practice. Serious infusion-associated events manifested by dyspnea, hypotension, wheezing, bronchospasm, tachycardia, reduced oxygen saturation, or respiratory distress should be managed with supportive therapies as clinically indicated (e.g. supplemental oxygen and  $\beta_2$ -adrenergic agonists).

Systemic corticosteroids and TNF $\alpha$  inhibitors may attenuate potential beneficial immunologic effects of treatment but may be administered at the discretion of the treating physician. If feasible, alternatives to corticosteroids should be considered. Premedication may be administered for Cycles  $\geq$  2 at the discretion of the treating physician. The use of inhaled

corticosteroids and mineralocorticoids (e.g., fludrocortisone) for patients with orthostatic hypotension or adrenocortical insufficiency is allowed. Megastrol administered as appetite stimulant is acceptable while the patient is enrolled in the study.

Patients who use oral contraceptives, hormone-replacement therapy, prophylactic or therapeutic anticoagulation therapy (such as low-molecular-weight heparin or warfarin at a stable dose level), or other allowed maintenance therapy should continue their use. Males and females of reproductive potential should use highly effective means of contraception.

## 7.2 Excluded Therapy

Any concomitant therapy intended for the treatment of cancer, whether health authority-approved or experimental, is prohibited. This includes but is not limited to the following:

- Chemotherapy, hormonal therapy, immunotherapy, radiotherapy, investigational agents, or herbal therapy
  - After day 29, certain forms of radiotherapy may be considered for palliation if patients are deriving benefit (e.g., treatment of known bony metastases); ERS administration should be continued during such palliative radiotherapy.

It is strongly recommended that:

- Traditional herbal medicines not be administered because the ingredients of many herbal medicines are not fully studied and their use may result in unanticipated drug-drug interactions that may cause, or confound assessment of, toxicity

Patients are not allowed to receive immunostimulatory agents, including but not limited to IFN- $\alpha$ , IFN- $\gamma$ , or IL-2, during the entire study. These agents, in combination with study treatment, could potentially increase the risk for autoimmune conditions.

Patients should also not be receiving immunosuppressive medications, including but not limited to cyclophosphamide, azathioprine, methotrexate, and thalidomide. These agents could potentially alter the activity and the safety of ERS therapy. Systemic corticosteroids and anti-TNF $\alpha$  agents may attenuate potential beneficial immunologic effects of the ERS therapy but may be administered at the discretion of the treating physician and if needed to manage treatment toxicity per guidelines outlined in this protocol. If feasible, alternatives to these agents should be considered.

In addition, all patients (including those who discontinue the study early) should not receive other immunotherapy agents for at least 14 days after discontinuing study therapy.

Subjects are prohibited from receiving the following therapies starting from study treatment initiation through end of treatment phase of this study unless otherwise noted below:

- Any investigational medication other than the study drugs.
- Any chronic immunological-suppressive treatment for any reason. (**Note:** Inhaled or topical steroids are allowed, and systemic steroids at doses  $\leq 10$  mg/day prednisone or equivalents are allowed and immune suppressants are allowed for short-term treatment for immune toxicities or as prophylaxis for contrast allergy for imaging procedures.)
- Administration of a live attenuated vaccine within 30 days before the first dose of study treatment and while participating in the study. Examples of live vaccines include, but are not limited to, the following: measles, mumps, rubella, chicken pox, yellow fever, rabies, BCG, and typhoid vaccine. Seasonal influenza vaccines for injection are generally killed virus vaccines and are allowed; however, intranasal influenza vaccines (eg, FluMist®) are live attenuated vaccines and are not allowed.
- Use of any MAOI or drug associated with significant MAOI activity agents is prohibited from 21 days prior to Day 1 through 2 weeks after the final dose of epacadostat has been administered
- Use of any immunological-based treatment for any reason from study treatment initiation through follow-up visit is prohibited.
- Note: Completed adjuvant therapy (eg, vaccines) with medical monitor approval, inhaled or topical steroids, and systemic steroids at doses  $\leq 10$  mg/day prednisone equivalents are allowed, as described in Restricted Medications.
- Any UGT1A9 inhibitor, including acitretin, amitriptyline, androsterone, cyclosporine, dasatinib, diclofenac, diflunisal, efavirenz, erlotinib, estradiol (17-beta), flutamide, gefitinib, gemfibrozil, glycyrrhetic acid glycyrrhizin, imatinib, imipramine, ketoconazole, linoleic acid supplements, mefenamic acid, mycophenolic acid, niflumic acid, nilotinib, phenobarbital, phenylbutazone, phenytoin, probenecid, \*propofol, quinidine, ritonavir, sorafenib, sulfapyrazone, valproic acid, and verapamil.
- *\*Note – Propofol, when used for short-term sedation during surgical/biopsy procedures, is allowed. The epacadostat dose may be taken on the morning of the procedure, and the evening dose held following the procedure. Epacadostat may be resumed the next day*

Subjects may receive other medications that the investigator deems to be medically necessary.

The exclusion criteria describe other medications that are prohibited during this study. There are no prohibited therapies during the post-treatment follow-up phase.

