#### **4.2 Exclusion Criteria**

1. Uncontrolled concomitant disease that in the opinion of the investigator would interfere with the patient's safety or compliance on trial.
2. Significant cardiovascular disease (NYHA Class II or greater); myocardial infarction within 3 month prior to randomization, unstable arrhythmias, unstable angina or a patient with a known LVEF (Left Ventricular Ejection Fraction)  $< 40\%$
3. Severe infection that in the opinion of the investigator would interfere with the patients safety or compliance on trial within 2 weeks prior to enrollment. Oral or IV antibiotics within 2 weeks or 5 half-lives prior to enrollment.
4. Active tuberculosis
5. History of severe autoimmune disease that in the opinion of the investigator would interfere with patient safety or compliance on trial.

6. Positive for Human Immunodeficiency Virus (HIV), Hepatitis B (Hepatitis B Surface Antigen [HBsAg] reactive), or Hepatitis C virus (Hepatitis C Virus Ribonucleic Acid [HCV RNA] (qualitative) is detected)
7. Previous treatment with epacadostat, SD-101, or any other IDO inhibitor or CpG molecule.
8. Treatment with systemic corticosteroids or other systemic immunosuppressive medications within past 4 weeks or 5 half-lives whichever is shorter. Use of inhaled or topical steroids or systemic corticosteroids < 10 mg/ day of prednisone (or equivalent) is permitted.
9. Pregnant and/or lactating women.
10. Evidence of active interstitial lung disease or active non-infectious pneumonitis
11. Receipt of live attenuated vaccine within 30 days before the first dose of study treatment.
12. Use of any UGT1A9 inhibitor while on active study treatment, including the following: diclofenac, imipramine, ketoconazole, mefenamic acid, and probenecid.
13. Known allergy or reaction to any component of either study drug formulation.
14. Subjects receiving Monoamine Oxidase Inhibitors (MAOIs) or drug which has significant MAOI activity (meperidine, linezolid, methylene blue) from 21 days prior to Day 1 through 2 weeks after the final dose of epacadostat has been administered.
15. Any history of Serotonin Syndrome (SS) after receiving serotonergic drugs.
16. Known contraindications to radiotherapy including but not limited to radiation sensitivity syndromes such as xeroderma pigmentosum and ataxia telangiectasia mutated.

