### 8.1 Duration of Follow Up

All patients will be followed for 30 days after the last dose of treatment with the agent under this IND or until all treatment related clinical significant toxicities resolve to baseline or grade  $\leq 1$ . Adverse events with attribution of possible, probable or definite will be reported following guidelines for adverse event reporting and all SAEs will be reported for 30 days after the last dose. Patients will be followed every 3 months per standard of care for PFS and OS.

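### The closing sentence of 7.2 lifts all drug bans in follow-up although two dated bans run past the last dose, and 7.1 lets estradiol users continue a drug that 7.2 prohibits

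*Combined protocol and SAP*

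**What the plan says.** **After the last dose.** Section 7.2 closes with "There are no prohibited therapies during the post-treatment follow-up phase". The sentence carries no exception. The prohibited-therapy list in 7.2 applies by default "starting from study treatment initiation through end of treatment phase of this study unless otherwise noted below". One item in that list, MAOIs and drugs with significant MAOI activity, does state a later end. Exclusion criterion 14 in section 4.2 repeats it: the ban runs "from 21 days prior to Day 1 through 2 weeks after the final dose of epacadostat has been administered". Above the list, 7.2 also says that all patients, including those who leave early, "should not receive other immunotherapy agents for at least 14 days after discontinuing study therapy". A further list item reads "Use of any immunological-based treatment for any reason from study treatment initiation through follow-up visit is prohibited", with no day given for that visit.

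**When follow-up begins.** Section 8.1: "All patients will be followed for 30 days after the last dose of treatment with the agent under this IND", or until treatment-related toxicities settle. Footnote l of the study calendar (9.1) says much the same under the follow-up column, then adds data collection every 3 months. No section defines the phase named in the closing sentence.

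**Hormone replacement.** Section 7.1 lists users of hormone replacement, among others, and says they should carry on. Section 7.2 includes 17-beta estradiol among the prohibited UGT1A9 inhibitors; the only exception there is short-term propofol. Exclusion criterion 12 bars any UGT1A9 inhibitor on active treatment, but its five named examples do not include estradiol.

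**The concern.** These are instructions that sites act on. A patient who stops for progression may be considered for another immunotherapy within days, and one who develops an infection may be considered for linezolid, which exclusion 14 names as having MAOI activity. The closing sentence clears both at once. The dated rules hold both back for 14 days. A site that follows the closing sentence literally gives a drug that the protocol bans.

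The estradiol point works the same way during treatment. Staff who screen from section 4.2 and advise from 7.1 could enrol an estradiol user, tell her to continue, and create a deviation that shows only in the long list in 7.2. The pathway is one the protocol treats as relevant: section 2.4.2 says that UGT1A9 forms M9, a major metabolite of epacadostat.

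**Working it through.** The check is mainly a comparison of texts. The plan gives no figure to reproduce on this point.

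**Step 1. Days barred after the last dose, by rule**

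| Rule | Where | Days barred after last dose |
|---|---|---|
| Closing sentence, if the phase starts at the last dose | 7.2 | 0 |
| MAOIs | 7.2 and exclusion 14 | 14 |
| Other immunotherapy | 7.2 | at least 14 |
| Immunological-based treatment | 7.2 | to an undated follow-up visit |

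The first row conflicts with the second and third for 14 days. The MAOI end-point looks deliberate: the list allows items to depart from its default end, this item does so, and exclusion 14 repeats the same dates. The 14-day immunotherapy rule concerns only the time after discontinuation, so a reading under which nothing is barred then leaves it without content.

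**Step 2. Does the phase start at the last dose?** Section 8.1 and footnote l both count follow-up from the last dose. Section 3, section 8.1 and footnote l also describe a later 3-monthly collection. If the phase meant only that later period, both 14-day bans would have expired and the conflict would be gone. Nothing in the text restricts the term in this way.

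**Step 3. How much drug is left?** Input: half-life 2.9 h (section 2.4.4.1, Study INCB 24360-101). Assumption: simple exponential decline. Fraction remaining at t hours = 0.5^(t/2.9).

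- t = 12: 0.5^(12/2.9) = 0.057, or 5.7%.
- t = 24: 0.5^(24/2.9) = 0.003, or 0.3%.
- Five half-lives: 5 × 2.9 = 14.5 h.

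On this assumption, any serotonin concern that depends on circulating epacadostat falls mainly in the first day. Section 2.4.3.1 already describes the syndrome as a theoretical risk.

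**Step 4. Estradiol.** In 7.1, hormone replacement appears as a class with an instruction to continue. In 7.2, one member of that class is prohibited, with no exception for replacement use. The two instructions cannot both be followed by a patient whose product contains 17-beta estradiol. They can be by everyone else. The documents give no change in epacadostat exposure with estradiol, so the effect cannot be estimated.

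**The case against.** The best defence has three parts.

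1. *A specific rule beats a general one.* The MAOI ban is dated, drug-specific and stated twice, and the sentence just before the closing one sends the reader to the exclusion criteria. Most sites would follow the dated rule. This stands as a reason to expect little harm. It does not make the closing sentence correct.

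2. *A coherent sequence is possible.* The treatment phase ends, some items extend a little beyond it, and then the phase with no bans begins, meaning the 3-monthly collection. This is the strongest reply. It would remove the post-dose conflict, but it needs a definition that the protocol does not give and that 8.1 and footnote l point away from.

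3. *Section 7.1 covers only allowed products.* Its sentence ends with a reference to other permitted maintenance treatment. Warfarin is likewise named there as continuing and then restricted in 7.3. Hormone replacement is also wider than estrogen, since inclusion criterion 12 admits patients on stable thyroid replacement or on replacement for adrenal insufficiency. All of that is fair, and it is why the point is confined to estradiol. Section 7.1 still names the class without qualification and without pointing to 7.2.

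A reader might go further and infer that the two immunotherapy rules in 7.2 contradict each other. They do not. The 14 days are a minimum, so keeping to the longer rule satisfies both. The undated follow-up visit is a missing definition only. The size of any gap would rest on an assumed visit day.

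**Conclusion.** The point holds on the current text, in two parts. The closing sentence of 7.2 contradicts two dated bans for 14 days after the last dose, unless the undefined phase is taken to mean the 3-monthly collection. Section 7.1 conflicts with 7.2 and exclusion 12 for users of 17-beta estradiol.

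The consequence is small. The decay figures assume exponential decline from one reported half-life, and the estradiol effect is unquantified. The documents do not say how many patients would be considered for these drugs. Nothing here touches sample size, error rates or the Simon two-stage designs.

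Two wider readings should be resisted.

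- A reader might add immunostimulatory agents and live vaccines to the bans that outlast treatment. The first are barred "during the entire study. These agents, in combination with study treatment, could potentially increase the risk for autoimmune conditions", a reason tied to concurrent treatment; the second are covered by "Administration of a live attenuated vaccine within 30 days before the first dose of study treatment and while participating in the study". Neither states an end-point after the last dose, so neither shows a deliberate post-treatment ban.
- A reader might express the conflict as a share of the 30-day follow-up. That period is not fixed, because 8.1 lets it run until toxicities resolve, and a share of days says nothing about how many patients are affected.

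**What to change.** Make two wording changes in one amendment.

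(a) **Section 7.2, last sentence.** Open it with: *Except for restrictions above or in the exclusion criteria that state an end-point after the last dose (MAOIs; other immunotherapy),* and leave the rest unchanged. Do not add immunostimulatory agents or live vaccines to the exception. That would create a post-treatment ban with no stated end, and interferon or IL-2 could then fall under two rules with different ends.

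(b) **Section 7.1, after the mention of hormone replacement.** Insert: *(except products prohibited in 7.2, e.g. 17-beta estradiol, which must be stopped or switched before Day 1)*.

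Optionally, state the day of the follow-up visit named in 7.2.

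The cost is slight. Visits, sample size and analysis do not change. Any patient using estradiol would have to switch or stop at screening, which 7.2 already requires.

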**7.3 Restricted Medications/Treatment**

- Systemic steroids may be used at doses  $\leq 10$  mg/day prednisone or equivalents.
- Use of coumarin-based anticoagulants (eg, Coumadin) is discouraged. Low-dose Coumadin® (1 mg) is acceptable; however, doses that increase the INR are discouraged and will require dose modification. If an alternative to coumarin-based anticoagulants cannot be used, dose modifications of the Coumadin® may be needed. Based on the observed magnitude of epacadostat/warfarin PK interaction and PK/PD modeling results, for an epacadostat dose of 300 mg BID, the dose of warfarin should be reduced by approximately one-third after initiation of epacadostat administration based on approximately 30% to 40% reduction in S- and R-warfarin oral clearance values. Close INR monitoring is recommended for subjects on a stable dose of warfarin who are starting treatment with epacadostat. Based on PK/PD modeling, recommendations for warfarin dose modifications for subjects receiving other epacadostat doses, are summarized in Table 7 based on the INR prior to starting epacadostat.

**Table 7: Warfarin dose modifications with Epacadostat**

Stable Baseline INR	Epacadostat Dose		
	$\leq 50-100$ mg BID	200 mg BID	300 mg BID
INR $\leq 2.5$	Close INR monitoring	Close INR monitoring	Reduce warfarin by ~33% and monitor INR
INR $> 2.5$	Close INR monitoring	Reduce warfarin by 20%-25% and monitor INR	Reduce warfarin by ~33% and monitor INR

- Use of the anticonvulsant carbamazepine (a UGT1A9 inducer) is discouraged. Because there is a potential interaction that could result in lower epacadostat exposures, an alternative to carbamazepine should be used, if possible.

## 8. TREATMENT DURATION

Patients will complete therapy unless one of the following criteria applies:

- Confirmed Disease progression per irRECIST
- Intercurrent illness that prevents further administration of treatment
- Unacceptable adverse events or DLT
- Patient withdrawal from study (patient choice)
- Pregnancy
- Delay in epacadostat treatment > 30 days due to toxicity
- Failure of patient to adhere to study requirements
- Physician Discretion

### 8.1 Duration of Follow Up

All patients will be followed for 30 days after the last dose of treatment with the agent under this IND or until all treatment related clinical significant toxicities resolve to baseline or grade  $\leq 1$ . Adverse events with attribution of possible, probable or definite will be reported following guidelines for adverse event reporting and all SAEs will be reported for 30 days after the last dose. Patients will be followed every 3 months per standard of care for PFS and OS.

### 8.2 Discontinuation Due to Disease Progression

Immunotherapeutic agents such as epacadostat and SD-101 may produce antitumor effects by potentiating endogenous cancer-specific immune responses. The response patterns seen with such an approach may extend beyond the typical time course of responses seen with cytotoxic agents and can manifest as a clinical response after an initial increase in tumor burden or even the appearance of new lesions.

Immune related RECIST will be used for assessment of tumor response for the purposes of managing subjects on Protocol treatment and decision making for discontinuation of study therapy due to disease progression. PD should be confirmed no earlier than 4 weeks later according to the criteria outlined in Table 8. Subjects who are deemed clinically unstable or who have biopsy proven new metastatic lesions are not required to have repeat imaging for confirmation. This decision will be based on clinical judgment of a subject's overall clinical condition, including performance status, clinical symptoms, and laboratory data. At a minimum, subjects must meet the following criteria for continued treatment on study after disease progression is identified at a tumor assessment:

When feasible, subjects should not be discontinued until progression is confirmed; however, the decision to continue study treatment after the first evidence of disease progression is at the investigator's discretion based on the clinical status of the subject.

Subjects may receive study treatment while waiting for confirmation of PD if they are clinically stable as defined by the following criteria:

- No decline in ECOG performance status.
- Absence of new or worsening symptoms.
- Absence of rapid progression of disease.
- Absence of progressive tumor at critical anatomical sites (e.g., spinal cord compression) requiring urgent alternative medical intervention.

